5.2 Trial Treatment(s)

The treatments to be used in this trial are outlined below in. A cycle of treatment in this protocol is defined as six weeks, except as noted in the table.

Table 9 Trial Treatment

Drug	Dose/Potency	Dose Frequency	Route of Administration	Regimen/Treatment Period	Use
Pembrolizumab	1mg/kg*	Q3W	IV infusion	Days 1 and 22 of each cycle in Parts 1, 2, or 3	Experimental
Pembrolizumab	2mg/kg	Q3W	IV infusion	Days 1 and 22 of each cycle in Parts 1, 2, or 3	Experimental
Pembrolizumab	200 mg	Q3W	IV infusion	Days 1 and 22 of each cycle in Parts 4 or 5, with the exception of Cycle 1**	Experimental
Placebo (saline IV)	--	Q3W	IV infusion	Days 1 and 22 of each cycle	Experimental
Trametinib	1.5mg*	1.5mg QD	Oral	Day 1 up until study treatment discontinuation	Experimental
Trametinib	2mg	2mg QD	Oral	Day 1 up until study treatment discontinuation	Experimental
Dabrafenib	150mg*	75mg BID	Oral	Day 1 up until study treatment discontinuation	Experimental
Dabrafenib	200mg*	100mg BID	Oral	Day 1 up until study treatment discontinuation	Experimental
Dabrafenib	300mg	150mg BID	Oral	Day 1 up until study treatment discontinuation	Experimental

*Dose/Potency activated only in the event dose reduction required.

**Cycle 1 in Parts 4 and 5 are longer in length due to trametinib run-in of two or four weeks.

For dosing regimens initiating with four weeks of trametinib monotherapy, pembrolizumab dosing occurs on Days 29 and 50. For dosing regimens initiating with two weeks of trametinib monotherapy, pembrolizumab dosing occurs on Days 15 and 36.

Please note, the term ‘study treatment’ is used throughout the protocol to describe any combination of products received by the subject as per the protocol design. Study treatment may therefore refer to the individual study treatments or a combination of those study treatments.

Trial treatment should begin on the day of randomization or as close as possible to the date on which the subject is allocated/assigned.

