5.2.1.2.1 Dose Modification and Toxicity Management Guidelines for Pembrolizumab

Dose modification and toxicity management for immune-related AEs associated with pembrolizumab

AEs associated with pembrolizumab exposure may represent an immunologic etiology. These immune-related AEs (irAEs) may occur shortly after the first dose or several months after the last dose of pembrolizumab treatment and may affect more than one body system simultaneously. Therefore, early recognition and initiation of treatment is critical to reduce complications. Based on existing clinical study data, most irAEs were reversible and could be managed with interruptions of pembrolizumab, administration of corticosteroids and/or other supportive care. For suspected irAEs, ensure adequate evaluation to confirm etiology or exclude other causes. Additional procedures or tests such as bronchoscopy, endoscopy, skin biopsy may be included as part of the evaluation. Based on the severity of irAEs, withhold or permanently discontinue pembrolizumab and administer corticosteroids. Dose modification and toxicity management guidelines for irAEs associated with pembrolizumab are provided in [Table 10](#) below and in Section 5.6. See Section 5.6 for detailed supportive care guidelines, including use of corticosteroids for specific AEs.

Table 10 Dose Modification and Toxicity Management Guidelines for Immune-related AEs Associated with Pembrolizumab

General instructions:				

 1. Corticosteroid taper should be initiated upon AE improving to Grade 1 or less and continue to taper over at least 4 weeks. 2. For situations where pembrolizumab has been withheld, pembrolizumab can be resumed after AE has been reduced to Grade 1 or 0 and corticosteroid has been tapered. Pembrolizumab must be permanently discontinued if AE does not resolve within 12 weeks of last dose or corticosteroids cannot be reduced to ≤ 10 mg prednisone or equivalent per day within 12 weeks. 3. For severe and life-threatening irAEs, IV corticosteroid should be initiated first followed by oral steroid. Other immunosuppressive treatment should be initiated if irAEs cannot be controlled by corticosteroids. 				
Immune-related AEs	Toxicity grade or conditions (CTCAEv4.0)	Action taken to pembrolizumab	irAE management with corticosteroid and/or other therapies	Monitor and follow-up

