Pneumonitis (see also Table 22)	Grade 2	Withhold	
 • Administer corticosteroids (initial dose of 1-2 mg/kg prednisone or equivalent) followed by taper 	
 • Monitor participants for signs and symptoms of pneumonitis • Evaluate participants with suspected pneumonitis with radiographic imaging and initiate corticosteroid treatment • Add prophylactic antibiotics for opportunistic infections
	Grade 3 or 4, or recurrent Grade 2	Permanently discontinue		
Diarrhea / Colitis (see also Table 18)	Grade 2 or 3	Withhold	
 • Administer corticosteroids (initial dose of 1-2 mg/kg prednisone or equivalent) followed by taper 	
 • Monitor participants for signs and symptoms of enterocolitis (ie, diarrhea, abdominal pain, blood or mucus in stool with or without fever) and of bowel perforation (ie, peritoneal signs and ileus). • Participants with \geq Grade 2 diarrhea suspecting colitis should consider GI consultation and performing endoscopy to rule out colitis. • Participants with diarrhea/colitis should be advised to drink liberal quantities of clear fluids. If sufficient oral fluid intake is not feasible, fluid and electrolytes should be substituted via IV infusion.
	Grade 4	Permanently discontinue		

Immune-related AEs	Toxicity grade or conditions (CTCAEv4.0)	Action taken to pembrolizumab	irAE management with corticosteroid and/or other therapies	Monitor and follow-up
AST / ALT elevation or Increased bilirubin See also Section 5.6.1.1.15	Grade 2	Withhold See also Table 30	
 Administer corticosteroids (initial dose of 0.5-1 mg/kg prednisone or equivalent) followed by taper 	
 Monitor with liver function tests (consider weekly or more frequently until liver enzyme value returned to baseline or is stable)
	Grade 3 or 4	Permanently discontinue Note: For Grade 3 events see Table 30 for detailed management and dose modification guidelines based on specific hepatic laboratory abnormalities	
 Administer corticosteroids (initial dose of 1-2 mg/kg prednisone or equivalent) followed by taper 	

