5.2.2.1 Pembrolizumab Dose Administration

Pembrolizumab should be administered every 21 days (for Q3W schedule) after all procedures and assessments have been completed except for the post-infusion PK sample time points listed in the Study Flow Chart. Pembrolizumab may be administered within 72 hours before or after the planned date of treatment for administrative reasons only (e.g., scheduling an infusion around a holiday).

The specific time of pembrolizumab administration (e.g., time of the week for first administration; time of the day for each administration) should take into consideration PK sampling time points and study visit procedures.

Pembrolizumab will be administered as a 30 minute IV infusion Q3W. Sites should make every effort to target infusion timing to be as close to 30 minutes as possible. However, given the variability of infusion pumps from site to site, a window of -5 minutes and +10 minutes is permitted (i.e., infusion time is 30 minutes: -5 min/+10 min). Subjects do not need to be observed for any specific period of time after the infusion, but should be provided instructions to notify study personnel if symptoms of infusion reaction occur after any pembrolizumab infusion.

The Procedures/Pharmacy Manuals contain specific instructions for pembrolizumab dose calculation, preparation of the infusion fluid, and administration.

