Investigators should refer to the appropriate IB for trametinib, dabrafenib and pembrolizumab for additional information regarding the background of each drug and the management of other AEs or potential safety-related issues.

Events of Clinical Interest (ECIs) are selected non-serious and serious adverse experiences that must be reported to Merck **within 24 hours** regardless of attribution to trial treatment.

5.6.1.1 Pembrolizumab+Trametinib and/or Dabrafenib, or, Trametinib+Dabrafenib Combination Safety Management Guidelines

Dose modifications and stopping criteria for the management of toxicities are presented in this section for subjects treated with the combination of dabrafenib and/or trametinib +/- pembrolizumab. Toxicities common to dabrafenib, trametinib, and pembrolizumab include, but are not limited to, ocular toxicities, skin-related toxicities, diarrhea, pneumonitis, and pyrexia. Therefore, it is possible that these and/or other toxicities may be exacerbated when dabrafenib, trametinib, and pembrolizumab are combined. For this reason, it is important to note that the management guidelines for the combination of dabrafenib + trametinib + pembrolizumab may differ for a given AE from the management guidelines for single-agent dabrafenib, single-agent trametinib, combination of dabrafenib+trametinib, or single-agent pembrolizumab.

5.6.1.1.1 Dose Level Reduction of Trametinib and/or Dabrafenib for Subjects beyond the DLT Period

The dose level reductions for subjects beyond the DLT evaluation period for dabrafenib and trametinib for this study are provided in [Table 5](#) and [Table 16](#).

Table 16 Dose Level Reduction Guidelines

Dose Level	Dabrafenib Dose/Schedule	Trametinib Dose/Schedule
Starting Dose	150 mg BID	2 mg once daily
-1 (1 st Dose reduction)	100 mg BID	1.5 mg once daily
-2 (2 nd Dose reduction)	75 mg BID	1.0 mg once daily
Abbreviation: BID = twice daily		

If an AE resolves to grade 1 or baseline at the reduced dose level, and no additional toxicities are seen after 4 weeks of study treatment at the reduced dose, the dose may be increased to the previous dose level after discussion with the Sponsor. Please refer to Section 5.2.1.2.1 and Section 5.6.1.1 for additional information on dose modification and associated supportive care guidelines for pembrolizumab, trametinib, and/or dabrafenib.

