Grade 2	
 CT scan (high-resolution with lung windows) Consider frequent Chest X-ray for monitoring Clinical evaluation and laboratory work-up for infection Consult pulmonologist, consider Infectious Disease consultation Conduct in-person evaluation approximately twice per week Bronchoscopy with biopsy and/or BAL recommended Treat with systemic corticosteroids at a dose of 1 to 2 mg/kg/day prednisone or equivalent. When symptoms improve to Grade 1 or less, steroid taper (if systemic corticosteroids initiated) should be started and continued over no less than 4 weeks. 	
 Interrupt study all treatment until recovery to grade ≤ 1 Treatment with pembrolizumab may be resumed if the event improves to \leq Grade 1 within 12 weeks and corticosteroids have been reduced to the equivalent of methylprednisolone 10 mg PO daily or less. Repeat chest imaging monthly as clinically indicated. Treatment with dabrafenib and trametinib at one dose level reduction may be resumed if the event improves to \leq Grade 1 within 4 weeks; escalation to previous dose level after 4 weeks may be possible after discussion with sponsor If no recovery to grade ≤ 1 within 4 weeks or second episode of Grade 2 or higher pneumonitis on re-challenge, permanently discontinue all study treatment

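### Table 22, Grade 2 pneumonitis: for a first episode that recovers between week 4 and week 12, one bullet permits pembrolizumab to resume and another stops all study treatment, with no stated precedence

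*Combined protocol and SAP*

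**What the plan says.** The Grade 2 row of Table 22 interrupts all treatment until recovery to Grade 1 or less. Three rules then apply.

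- **Pembrolizumab** may resume if the event improves to Grade 1 or less "within 12 weeks and corticosteroids have been reduced to the equivalent of methylprednisolone 10 mg PO daily or less".
- **Dabrafenib and trametinib** have their own limit: "Treatment with dabrafenib and trametinib at one dose level reduction may be resumed if the event improves to" Grade 1 or less within 4 weeks.
- **Permanent stop:** with no recovery to Grade 1 or less "within 4 weeks or second episode of Grade 2 or higher pneumonitis on re-challenge, permanently discontinue all study treatment".

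Section 5.2 says that the term study treatment "is used throughout the protocol to describe any combination of products received by the subject as per the protocol design". The stop bullet adds the word all, so it includes pembrolizumab.

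Section 5.6.1.1.8 refers to Tables 10 and 22 together and does not rank them. Table 10 says to withhold pembrolizumab for Grade 2 pneumonitis and reserves permanent discontinuation for "Grade 3 or 4, or recurrent Grade 2". Its general instructions add: "Pembrolizumab must be permanently discontinued if AE does not resolve within 12 weeks of last dose or corticosteroids cannot be reduced to" 10 mg prednisone or equivalent per day within 12 weeks. Table 10 has no 4-week limit.

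**The concern.** The 12-week permission and the 4-week stop are in the same cell and concern the same drug. If the stop always prevails, improvement between weeks 4 and 12 never permits resumption, and it is unclear why pembrolizumab was given a longer recovery limit than the kinase inhibitors. If the permission prevails, the word all in the stop bullet is wrong.

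The protocol does not choose between these, so two sites with the same patient can act differently. One may withdraw pembrolizumab permanently from a patient whom the other would re-treat. Table 22 also gives no start point for either limit.

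**Working it through.** The plan has no figure of its own to reproduce. The check is first logical, then a count of days.

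**Rules by time of recovery (first episode, steroids reduced as required)**

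| Recovery to Grade 1 or less | Pembrolizumab bullet | Dabrafenib/trametinib bullet | Stop bullet | Result |
|---|---|---|---|---|
| By week 4 | may resume | may resume, reduced | not triggered | consistent |
| After week 4, up to week 12 | may resume | may not resume | stop all | conflict for pembrolizumab |
| After week 12 | may not resume | may not resume | stop all | consistent |

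**Search for a rule of precedence**

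- Section 5.6.1 sends the reader to the algorithm for the combination or the single agent. For the combination that is Table 22, so it cannot settle a conflict inside Table 22.
- Section 5.6.1.1 warns that "the management guidelines for the combination of dabrafenib + trametinib + pembrolizumab may differ for a given AE" from single-agent guidance. This makes a stricter combination rule possible but does not state one.
- Section 5.6.1.1.2 lets subjects who stop one drug for toxicity stay on the others, but the Table 22 stop covers all of them.

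**Length of the overlap**

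Inputs: 4 weeks = 28 days and 12 weeks = 84 days (Table 22); the 12 weeks may run from the last dose (Table 10); dosing is every 21 days; and "Pembrolizumab may be administered within 72 hours before or after the planned date of treatment for administrative reasons only" (Section 5.2.2.1). Let t be the days from the last pembrolizumab dose to onset.

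1. Both limits from onset: 84 - 28 = 56 days.
2. 4 weeks from onset, 12 weeks from last dose: 84 - t - 28 = 56 - t days.
   - t = 0: 56 days.
   - t = 21 (nominal interval): 35 days.
   - t = 27 (one dose 3 days early, the next due 3 days late: 21 + 3 + 3): 29 days.
   - t = 56 or more: no overlap.

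These are upper bounds because they ignore steroids. The Grade 2 row starts steroids at 1 to 2 mg/kg/day and begins a taper of at least 4 weeks only once symptoms reach Grade 1. Assume that 10 mg is reached only at the end of a minimum 28-day taper, and must be reached within the same 12 weeks:

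3. Both from onset: recovery is needed by day 84 - 28 = 56, so the overlap is 56 - 28 = 28 days.
4. 12 weeks from last dose: 28 - t days, which is 28 at t = 0, 7 at t = 21 and 1 at t = 27. There is no overlap from t = 28.

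A faster fall to 10 mg gives values between the two sets.

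**The case against.** The strongest reply is that the bullets can be read together: recover by week 4 or stop everything; if recovered, resume pembrolizumab once steroids are down, within 12 weeks. Table 10 applies 12 weeks to steroid reduction as well as to resolution, and a patient who recovers by week 4 may well still be above 10 mg then. The reading makes clinical sense, but it does not fit the sentence, in which the 12 weeks qualify the improvement in the event. What stands is that the taper shortens the overlap.

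A reader might also infer more than the documents support:

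- *That the rule cannot be followed.* It can. One bullet permits and the other requires, so a site that stops satisfies both. What is unclear is whether the permission survives.
- *That patients could be re-exposed without oversight.* Section 5.6.1.1.2 requires sponsor contact before treatment resumes after more than 21 days of dabrafenib or trametinib interruption, and every overlap case exceeds 28 days. Section 5.6.1.3 asks for immediate discussion of immune-related events of Grade 2 or higher. These routes centralise the decision, although none says which limit applies.
- *That the 4-week stop is plainly a slip.* Table 10 and the separate limits per drug point that way. So does the Grade 3 rash row of Table 25, where the 4-week stop names only the kinase inhibitors. A deliberately stricter combination rule remains possible. The Grade 3 pneumonitis row does not help, since pembrolizumab is already permanently stopped there.

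**Conclusion.** The inconsistency is real and narrow. It concerns a first Grade 2 episode, treatment-related or not yet shown to be otherwise, that recovers after week 4 but within 12 weeks with steroids reduced, in a subject still receiving pembrolizumab. The consequence is early or uneven permanent loss of pembrolizumab.

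The overlap is at most 56 days, or 56 - t with the Table 10 clock, and about 28 or 28 - t days under the taper assumption. The start points are also assumptions, because Table 22 gives none.

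The documents give neither the event frequency nor the number of subjects still exposed. Section 8.2.1 allows Part 3 triplet subjects to continue under the toxicity guidelines, and Parts 4 and 5 allow pembrolizumab for up to 24 months, but the Part 5 expansion is closed, so the number may be small. Severity is minor to should-fix. No statistical result is affected.

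**What to change.** The sponsor should decide which limit governs pembrolizumab and make the bullets agree.

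**To align with Table 10**, replace the last Grade 2 bullet with:

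*If no recovery to Grade 1 or less within 4 weeks of onset, permanently discontinue dabrafenib and trametinib. If no recovery to Grade 1 or less within 12 weeks of the last pembrolizumab dose, or corticosteroids cannot be reduced to 10 mg/day or less of prednisone or equivalent within 12 weeks, permanently discontinue pembrolizumab. For a second episode of Grade 2 or higher on re-challenge, permanently discontinue all study treatment.*

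Also change the steroid level in the pembrolizumab bullet from methylprednisolone 10 mg to prednisone 10 mg or equivalent, so that the two tables match.

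**If the stricter rule was intended**, state that pembrolizumab may resume only if the event recovers to Grade 1 or less within 4 weeks of onset, and keep a separate 12-week limit for steroid reduction. Applying 4 weeks to both would all but bar resumption, given the minimum taper.

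The cost is one or two bullets in one table cell, by clarification letter or in the next amendment. Data collection and analysis do not change.

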5.6.1.1.9 Renal Events

Subjects should be carefully monitored for signs and symptoms of renal insufficiency (such as nephritis, renal failure, or creatinine elevations). All attempts should be made to rule out

other causes such as obstructive uropathy, progression of disease, or injury to other chemotherapy agents. A renal consultation is recommended.

Cases of renal insufficiency have occurred in subjects receiving dabrafenib and the combination of dabrafenib and trametinib, as well as in subjects receiving pembrolizumab. Prior to start of study treatment, concomitant medications should be reviewed for the potential risk of inducing nephrotoxicity and concomitant medications should be modified if clinically possible.

Guidelines regarding management and dose reduction for renal insufficiency considered to be related to study treatment by the investigator are provided in [Table 10](#) and [Table 23](#).

Table 23 Management and Dose Modification Guidelines for Renal Insufficiency

Serum Creatinine Level	Adverse Event Management	Action and Dose Modification
Serum creatinine increase >0.2 mg/dL (18 umol/L) but ≤ 0.5 mg/dL (44 umol/L) above baseline	
 • Recheck serum creatinine within 1 week • Serum creatinine increase > 1 week: contact Sponsor • For Grade 2 creatinine elevations, treat with prednisone 1-2 mg/kg p.o. daily (when symptoms improve to Grade 1 or less, steroid taper should be started and continued over no less than 4 weeks) • If pyrexia is present, treat pyrexia as per guidelines^a 	
 • Continue study treatment at the same dose level • For Grade 2 creatinine elevations, interrupt pembrolizumab
Serum creatinine increase >0.5 mg/dL (44 umol/L) above baseline or serum creatinine >2 mg/dL (> 177 umol/L)	
 • Monitor serum creatinine ≥ 2-times per week • Hospitalization may be necessary if serum creatinine cannot be monitored frequently • If pyrexia is present, treat pyrexia per guidelines^a • Consult nephrologist if clinically indicated • Perform ultrasound and/or renal biopsy if clinically indicated, for example: 
 1. Renal insufficiency persists despite volume repletion 2. Subject has new rash or signs of hypersensitivity (such as elevated eosinophil count) • For ≥ Grade 3 creatinine elevations, treat with systemic corticosteroids at a dose of 1 to 2 mg/kg prednisone or equivalent once per day. • When symptoms improve to Grade 1 or less, steroid taper should be started and continued over no less than 4 weeks. 	
 • Interrupt study treatment until serum creatinine recovers to baseline • Restart study treatment^b • For Grade 3-4 creatinine elevations, permanently discontinue pembrolizumab

Abbreviations: NSAIDs = non-steroidal anti-inflammatory drugs
 
a. NSAIDs can induce renal insufficiency, especially in subjects with dehydration; encourage oral fluids or consider intravenous fluids as clinically indicated. See guidelines for pyrexia.
 
b. Investigator may restart at either the same (pembrolizumab, dabrafenib and/or trametinib) or a reduced dose level (dabrafenib and/or trametinib). Escalation of study treatment to previous dose level is allowed if another episode of renal insufficiency does not occur after 4 weeks of dose reduction. Consultation with Sponsor is required before restarting study treatment if there is evidence of thrombotic microangiopathy.
		

5.6.1.1.10 Skin Events

Subjects should be carefully monitored for signs and symptoms of skin AEs, such as pruritis or rash. All attempts should be made to rule out other causes such as metastatic disease, infection or allergic dermatitis.

5.6.1.1.10.1 Rash

Rash is a frequent AE observed in subjects receiving trametinib, dabrafenib, or the combination of both therapies, as well as in subjects receiving pembrolizumab. Guidelines for rash management are based on experience with other MEK inhibitors and EGFR inhibitors [96, 97] and are provided below (Table 24 and Table 25).

Table 24 Guidelines for Supportive Care of Rash

Type of Care	Action
Prevention/Prophylaxis: Start from Day 1	
 Avoid unnecessary exposure to sunlight Apply broad-spectrum sunscreen (containing titanium dioxide or zinc oxide) with a skin protection factor (SPF) ≥ 15 at least twice daily. Sunscreen should be used during the day when exposed to the sun; emollient cream should be used at night or when not being exposed to the sun. Sunscreens should not be applied concomitantly with moisturizers such as emollient cream. Use thick, alcohol-free emollient cream (eg, glycerine and cetomacrogol cream) on dry areas of the body at least twice daily.
Symptomatic Care (rash): Start from Day 1 of rash and implement for a total of 6 weeks	
 Topical steroids and antibiotics should be applied once daily and more often as needed from Day 1. Use mild-strength topical steroid (hydrocortisone 1% cream) and topical antibiotic (eg, clindamycin) or oral antibiotics (eg, doxycycline 100 mg BID, minocycline 100 mg BID)
Symptomatic Care (other)^a	
 Pruritic lesions: cool compresses and oral antihistamine therapies Fissuring lesions: Monsel's solution, silver nitrate, or zinc oxide cream Desquamation: thick emollients and mild soap Paronychia: antiseptic bath, local potent corticosteroids in addition to oral antibiotics; if no improvement, consult dermatologist or surgeon Infected lesions: appropriate bacterial/fungal culture-driven systemic or topical antibiotics
Abbreviations: BID = twice daily; SPF = sun protection factor	
a. Subjects who develop rash/skin toxicities should be seen by a qualified physician and should receive evaluation for symptomatic/supportive care management	

Immediate Evaluation for Potential Skin ECIs

A. Photographs:

Every attempt should be made to get a photograph of the actual skin lesion or rash as soon as possible. Obtain appropriate consent for subject photographs if a consent form addendum is required by your IRB/ERC.

- Take digital photographs of:
 - o the head (to assess mucosal or eye involvement),
 - o the trunk and extremities, and
 - o a close-up of the skin lesion/rash.
- If possible, a ruler should be placed alongside the site of a skin occurrence as a fixed marker of distance.
- The time/date stamp should be set in the 'ON' position for documentation purposes.
- Photographs should be stored with the subject's study records.
- The Sponsor may request copies of photographs. The local study contact (e.g., CRA) will provide guidance to the site, if needed.

B. Past Medical History:

Collect past medical history relevant to the event, using the questions in Appendix 12.11 (Past Medical History Related to Dermatologic Event) as a guide. Any preexisting conditions not previously reported (e.g., drug allergy) should be entered into the Medical History eCRF.

C. Presentation of the Event:

Collect information on clinical presentation and potential contributing factors using the questions in Appendix 12.12 (Presentation of the Dermatologic Event) as a guide. This information should be summarized and entered in narrative format in the AE eCRF. Please use the available free-text fields, such as Signs and Symptoms. Note pertinent negatives where applicable to reflect that the information was collected. Any treatments administered should be entered on the Concomitant Medication eCRF.

D. Vitals Signs and Standard Laboratory Tests:

Measure vital signs (pulse, sitting BP, oral temperature, and respiratory rate) and record on the Vital Signs eCRF. Perform standard laboratory tests (CBC with manual differential and serum chemistry panel, including LFTs).

E. Focused Skin Examination:

Perform a focused skin examination using the questions in Appendix 12.13 (Focused Skin Examination) as a guide. Information should be summarized and entered on the Adverse Experience eCRF as part of the narrative.

F. Dermatology Consult

Refer the subject to a dermatologist as soon as possible.

- For a “severe rash”, the subject must be seen within 1-2 days of reporting the event.
- For clinically significant rash, the subject should be seen within 3-5 days.

The dermatologist should submit a biopsy sample to a certified dermatopathology laboratory or to a pathologist experienced in reviewing skin specimens.

The site should provide the dermatologist with all relevant case history, including copies of clinical photographs and laboratory test results.

Guidelines for management and dose reduction for rash considered to be related to study treatment are provided in [Table 25](#).

Table 25 Management and Dose Modification Guidelines for Rash

CTCAE Grade	Adverse Event Management	Action and Dose Modification (apply to both Dabrafenib and Trametinib for Part 3 and to Trametinib only for Part 4 and 5)
Grade 1	
 • Initiate prophylactic and symptomatic treatment measures. • Consider use of topical glucocorticosteroids (eg, betamethasone 0.1% cream or hydrocortisone 1%) or urea-containing creams in combination with oral antipruritics (eg, diphenhydramine HCl or hydroxyzine HCl) or moderate strength topical steroid^a • Reassess after 2 weeks 	
 • If tolerable, continue study treatment at the same dose. • If intolerable despite best supportive care, reduce dabrafenib and/or trametinib by one dose level^c
Grade 2	
 • Initiate prophylactic and symptomatic treatment measures • Use moderate strength topical steroid^a • Reassess after 2 weeks • Treatment with oral steroids at the physician’s discretion 	
 • If tolerable, continue study treatment at the same dose. • If intolerable despite best supportive care, reduce dabrafenib and/or trametinib by one dose level. If rash recovers to ≤Grade 1 within 2 weeks, resume dabrafenib and/or trametinib at previous dose level^c • If intolerable despite dose reduction interrupt dabrafenib and/or trametinib until recovery to ≤Grade 1, then restart at the reduced dose^b • Consider holding pembrolizumab
Grade 3	
 • Use moderate strength topical steroids^a PLUS oral steroids (eg, methyl-prednisolone dose pack, 1 mg/kg prednisone or equivalent once per day, or dexamethasone 4 mg four times orally daily). When symptoms improve to Grade 1 or less, steroid taper should be started and continued over no less than 4 weeks. • Consult dermatologist, consider biopsy 	
 • Interrupt all study treatments until rash recovers to Grade ≤1 • Restart^b pembrolizumab (after appropriate steroid tapering) and reduce dabrafenib and/or trametinib by one dose level^c • If no recovery to Grade ≤2 within 4 weeks, permanently discontinue dabrafenib and/or trametinib • Consider discontinuing pembrolizumab
Grade 4	
 • Same as Grade 3 	
 • Permanently discontinue all study treatment

Abbreviations: CTCAE = Common Terminology Criteria for Adverse Events.
 
a. Moderate-strength topical steroids: hydrocortisone 2.5% cream or fluticasone propionate 0.5% cream
 
b. Approval of Sponsor is required to restart study treatment after ≥21 days of interruption.
 
c. Escalation of study treatment to previous dose level may be considered if either improvement of Grade 1 rash per investigators’ judgment or no rash is evident 4 weeks after dose reduction or after restarting study treatment.
		

5.6.1.1.10.2 Hand-Foot Skin Reactions (HFSR)

Episodes of Hand-foot Skin Reaction (HFSR) have been observed in subjects receiving dabrafenib. Guidelines for management of HFSR are based on experience with other kinase inhibitors [98, 99].

Lifestyle modification: avoidance of hot water, traumatic activity, constrictive footwear, or excessive friction on the skin and the use of thick cotton socks and gloves, and shoes with padded insoles

Symptomatic treatments: apply moisturizing creams frequently, topical keratolytics (e.g. urea 20-40 % cream, salicylic acid 6%, tazarotene 0.1% cream, fluorouracil 5% cream), clobetasol propionate 0.05% ointment for erythematous areas, topical lidocaine 2%, and / or systemic pain medication such as non-steroidal anti-inflammatory drugs, codeine, and pregabalin for pain.

Dose modification may also be required. Refer to [Table 24](#) for rash guidelines.

5.6.1.1.10.3 New Malignancies

Cutaneous squamous cell carcinoma and keratoacanthoma have been observed in subjects treated with dabrafenib and the combination of dabrafenib and trametinib (see dabrafenib and trametinib combination IB). These treatment-related cuSCC should be surgically removed according to institutional practice. Dose modifications or interruptions of the study treatment are not required for cuSCC. Occurrence of cuSCC must be reported as an SAE.

New cutaneous and non-cutaneous malignancies that are reported to the Investigator should be reported as a SAE, excluding basal cell carcinoma. A biopsy of the new malignancy should be taken, where possible, and submitted for further analyses. Testing of these biopsies may include RAS mutation testing and analysis of proteins related to the action of dabrafenib. Genomic alterations, which include but not limited to DNA, RNA and protein analysis of these biopsy specimens may be performed, and would be restricted to the analysis of pathway mutations known to be associated with, and relevant to, BRAF-mutant tumors or pathway activation. Following discontinuation of dabrafenib, monitoring for non-cutaneous secondary/recurrent malignancies should continue every 3 months for up to 6 months or until initiation of another anti-neoplastic therapy.

5.6.1.1.10.4 Severe Cutaneous Adverse Reactions

Cases of Severe Cutaneous Adverse Reactions (SCARs), including Stevens-Johnson syndrome, and Drug Reaction with Eosinophilia and Systemic Symptoms, which can be life-threatening or fatal, have been reported during treatment with dabrafenib in combination with trametinib. Before initiating treatment, subjects should be advised of the signs and symptoms and monitored closely for skin reactions. If signs and symptoms suggestive of SCARs appear, dabrafenib and trametinib should be permanently discontinued.

